10.12.3 Amended protocol 03 (06 July 2023)

This amended protocol (amendment 03) is considered to be substantial based on the criteria set forth in Article 10(a) of Directive 2001/20/EC of the European Parliament and the Council of the European Union.

Overall rationale for the amendment

The main purpose of the protocol amendment 03 is to clarify exclusion of participants with a history of alcohol abuse and to limit consumption of alcohol during the course of the study.

Protocol amendment summary of changes table

Section # and Name	Description of change	Brief rationale
5.2 Exclusion criteria	Specifying exclusion of participants with history of alcohol abuse	Minimize the risk of liver injury caused by history of alcohol dependence/abuse
5.3.2 Lifestyle considerations, caffeine, alcohol and tobacco	Limit for daily consumption of alcohol while in the study	Minimize exposure to alcohol during the study, to not exacerbate potential liver injury risks of SAR443820
10.12 Appendix 12: Protocol amendment history	Updated to reflect current amended protocol.	Update.
Throughout	Minor editorial, typographical error corrections and document formatting revisions. Updates according to Sponsor's style guide.	Minor, therefore have not been summarized.

1	12-Jul-2024	
This version of SAP includes the following changes compared to the amended protocol 04:
 
For the analysis of sNfL, replace baseline MS type (RMS versus PMS) with the randomization stratification factor MS clinical subtype (RRMS, SPMS, or PPMS) in the MMRM model and exclude MS type by visit interaction from the covariates. For the analyses of new Gd-enhancing T1 lesions and new/enlarging T2 lesions, replace baseline MS type (RMS versus PMS) with the randomization stratification factor MS clinical subtype (RRMS, SPMS, or PPMS) in the negative binomial model.Remove the endpoints 'change from baseline in the total number and volume of non-enhancing lesions at Weeks 12, 24, 36, and 48' for Part A and 'change from baseline in the total number and volume of non-enhancing lesions at Week 96' for Part B as data for these endpoints were not collectedRemove the endpoints 'change from baseline in the intensity (T1) of slowly expanding lesions at Weeks 12, 24, 36 and 48' for Part A and 'change from baseline in the intensity (T1) of slowly expanding lesions to Week 96' for Part B as data for the corresponding endpoints were not collected.Change the confirmation period of time-to-event endpoints in Part B (ie, time to CDP, time to 20% increase in 9-HPT, time to 20% increase T25-FW test, and time to CCDP) from 12 weeks to 24 weeks.	Clarification

1 INTRODUCTION

1.1 STUDY DESIGN

Study ACT16753 is a Phase 2, randomized, double-blind, placebo-controlled, 2 parallel-arm study evaluating the effect of SAR443820 on serum neurofilament light chain (sNfL) levels in participants with multiple sclerosis, followed by an open-label, long-term extension period.

The study consists of 2 parts (A and B) as follows:

Part A is a 48-week, double-blind, placebo-controlled part, preceded by a screening period of up to 4 weeks before Day 1.

- The screening period will be up to 4 weeks and is designed to evaluate suitability for participation in the study in terms of MS diagnosis, clinical status based on EDSS, and safety screening evaluations. No IMP will be administered in this period.
- The double-blind treatment period will have a total duration of 48 weeks for each participant and will include the following:
 - Participants will be randomized at 1:1 ratio to receive SAR443820 20 mg QD (n = 84) or matching placebo QD (n = 84).
 - Randomization will be stratified by MS clinical subtypes (ie, RRMS, SPMS, or PPMS) in order to ensure a balance between the treatment and placebo arms within each MS clinical subtype. Participants will attend in-clinic study assessments at baseline (Day 1) and Weeks 2, 6, 12, 24, 36, and 48.

All participants who successfully completed Part A will be offered to rollover to Part B.

Participants who discontinue IMP during Part A, or who choose not to enter Part B will have their early discontinuation or safety follow-up visit, respectively, up to 2 weeks after the last dose of IMP.

Part B is an open-label, long-term extension of Part A. Part B starts from the end of Part A (Week 48) and continues up to Week 96.

- The assignment of participants to study intervention in Part A will remain double-blinded during Part B unless there is medical need to unblind the study intervention assignment.
- All participants will receive 20 mg QD SAR443820 in Part B.
- Participants will attend in-clinic study assessments at Weeks 52, 72, and 96 (and Week 48 which is the last visit of Part A and first visit of Part B); Week 50, 54, 56, 58, 60, 62, 64, 66, 68, 70, 76, 80, 84, 88, 92 visits for liver chemistry only may be conducted at local labs where available.

1.2 OBJECTIVES AND ENDPOINTS

Table 1 - Objectives and endpoints

Part A

	Objectives	Endpoints
Primary		
	
 To assess the effect of SAR443820 compared to placebo on serum Neurofilament light chain (sNfL) 	
 Week 48 sNfL levels relative to baseline
Secondary		
	
 To evaluate efficacy of SAR443820 compared to placebo on imaging and clinical endpoints 	
Cumulative number of new gadolinium (Gd)-enhancing T1 hyperintense lesions as detected by MRI at Week 48, defined as the sum of the individual number of new Gd-enhancing T1 hyperintense lesions at all scheduled visits starting after baseline up to and including the Week 48 visit
 
Cumulative number of new and/or enlarging T2 hyperintense lesions as detected by MRI, at Week 48, defined as the sum of the individual number of new and/or enlarging T2 lesions at all scheduled visits starting after baseline up to and including the Week 48 visit
 
Time to onset of 12 weeks confirmed disability progression (CDP) from baseline as assessed by the Expanded Disability Status Scale (EDSS) score
 
Time to onset of sustained 20% increase in 9-Hole Peg Test (9-HPT) confirmed over at least 12 weeks
 
Time to onset of sustained 20% increase in timed 25-foot walk test (T25-FW) confirmed over at least 12 weeks
 
Change from baseline in EDSS-Plus at Week 48
 
Annualized relapse rate (ARR) of RMS population (relapsing SPMS and RRMS) up to Week 48
 
Percent change from baseline in brain volume loss (BVL) as detected by brain MRI at 48 weeks
 
Change from baseline in the volume, number, and normalized intensity (T1) of slowly expanding lesions at Weeks 12, 24, 36, and 48
 
Change from baseline in the number of phase rim lesions (PRL) at Weeks 12, 24, 36, and 48; will be conducted at 3T capable sites
 
Incidence of AE, SAE, TEAE, PCSA in laboratory tests
 
Plasma concentration of SAR443820

Tertiary	
 To explore effect of SAR443820 compared to placebo on brain volume and chronic lesions To assess the safety and tolerability of SAR443820 To assess pharmacokinetic (PK) of SAR443820 	
 Change from baseline in sNfL level in MS subpopulations (RRMS, SPMS, PPMS) over 48 weeks

Objectives	Endpoints

subpopulations of multiple sclerosis (MS)
 
 • To assess the effect of SAR443820 compared to placebo on biomarkers of neurodegeneration, inflammation, and disease progression • To assess efficacy of SAR443820 compared to placebo on patient-reported outcomes (PROs) assessing the physical and psychological impact of MS from the patient's perspective (MSIS-29v2) and the impact of MS on the individual's walking ability (MSWS-12) 	
 • Change from baseline compared to Week 48 in: plasma chitinase-3-like protein 1 (CHI3L1), serum glial fibrillary acidic protein (sGFAP), interleukin-1B (IL1B), IL6, IL8, TNFα, Chemokine (C-C motif) ligands 3 (CCL3), and Chemokine (C-C motif) ligands 4 (CCL4) • Change from baseline in MSIS-29v2 physical and psychological domains scoring at Week 12, 24, 36, and 48 • Change from baseline in MSWS-12 at Week 12, 24, 36, and 48

Part B

Objectives	Endpoints

Primary
 
 • To assess long-term trends in durability of sNfL 
Secondary
 
 • To explore the effect of SAR443820 on brain volume and chronic lesions • To assess the long-term safety and tolerability of SAR443820 • To evaluate long-term effect of SAR443820 on disease progression and activity assessed by other clinical and imaging measures on physical function and patient-reported outcomes (PROs) 	
 • Week 96 sNfL levels relative to baseline • Percent change from baseline in BVL as detected by brain MRI at Week 96 • Change from baseline in volume, number and normalized intensity (T1) of slowly expanding lesions to Week 96 • Change from baseline in the number of PRLs (same participants/centers from Part A with 3T capability) at Week 96 • Incidence of AE, SAE, TEAE, PCSA in laboratory tests, ECG, and vital signs during through Week 96 • Cumulative number of new Gd-enhancing lesions as detected by T1-weighted MRI between 48 and 96 weeks; number of new or enlarging T2-hyperintense lesions on MRI at Week 96 relative to Week 48 • Annualized relapse rate (ARR) of RMS population (relapsing SPMS and RRMS) up to Week 96 • Time to onset of composite CDP (CCDP), confirmed over at least 24 weeks (6-month CCPD), by the EDSS Plus composite (EDSS score increase, OR 20% increase in the T25-FW test, OR 20% increase in the 9-HPT) • Time to onset of 24-week CDP as assessed by the EDSS score • Time to onset of sustained 20% increase in 9-HPT confirmed over at least 24 weeks • Time to onset of sustained 20% increase T25-FW test confirmed over at least 24 weeks

Objectives	Endpoints
	
 Change from baseline in EDSS-Plus at Week 96 Change in MSIS-29v2 physical and psychological domains scoring from baseline through Week 96 Change in MSWS-12 from baseline through Week 96

1.2.1 Estimands

Primary estimands defined for main endpoints in Part A are summarized in below [Table 2](#). More details are provided in [Section 3](#).

For all these estimands, the comparison of interest will be the comparison of SAR443820 vs. placebo.

Table 2 - Summary of primary estimand for main endpoints

Category	Endpoint	Population	Estimands	
			Intercurrent event(s) handling strategy	Population-level summary (analysis and missing data handling)
Primary objective: To assess the effect of SAR443820 compared to placebo on sNfL				
Primary endpoint (hypothetical strategy)	sNfL levels at Week 48 relative to baseline	miITT	Had IMP not been discontinued (hypothetical strategy), had baseline DMT not been permanently modified (hypothetical strategy)	Ratio of the geometric mean ratios compared to baseline between intervention groups from the mixed effect model with repeated measures (MMRM) on log-transformed data. Analysis will exclude data collected after the intercurrent events. Missing data will be handled by MMRM under the missing at random (MAR) assumption

Abbreviations: DMT = disease modifying therapy; IMP = investigational medicinal product; miITT = modified intent-to-treat; sNfL = serum neurofilament light chain

2 ANALYSIS POPULATIONS

The following populations for analyses are defined.

Table 3 - Populations for analyses

Population	Description
Screened	All participants who signed the ICF.
Randomized	All participants from screened population who have been allocated to a randomized intervention by IRT regardless of whether the intervention was received.
Exposed	All screened participants who take at least 1 dose of study intervention.
Randomized and treated	All randomized participants who take at least 1 dose of study intervention. Participants will be analyzed according to the intervention allocated by randomization.
Intent-to-treat (ITT)	All randomized participants. Participants will be analyzed according to the intervention allocated by randomization.
Modified ITT (mITT)	All participants from the ITT population who take at least 1 dose of study intervention and with an evaluable primary endpoint. The primary endpoint is evaluable when the following conditions are met: 
• The participant has a baseline and at least 1 post-baseline sNfL assessment before IMP discontinuation and before permanent modification of the background DMT.• Participants will be analyzed according to the intervention allocated by randomization.
Safety	All randomized participants who take at least 1 dose of study intervention. Participants will be analyzed according to the intervention they actually received.
Pharmacokinetic (PK)	All randomized and treated participants (safety population) with at least 1 post-baseline PK result with adequate documentation of dosing and sampling dates and times. Participants will be analyzed according to the intervention they actually received.

Abbreviations: DMT = disease modifying therapy; ICF = informed consent form; IRT = interactive response technology; sNfL = serum neurofilament light chain

Participants exposed to study intervention before or without being randomized will not be considered as randomized and will not be included in any analysis population. The safety experience of these participants will be reported separately.

Randomized participants for whom it is unclear whether they took the study intervention will be considered as exposed and will be included in the safety population as randomized.

For any participant randomized more than once, only the data associated with the first randomization will be used in any analysis population. The safety experience associated with any later randomization will be reported separately.

For participants receiving more than one study intervention during the study, the intervention group for as-treated analyses will be SAR443820 20 mg QD.

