6 STUDY INTERVENTION(S) AND CONCOMITANT THERAPY

Study intervention is defined as any investigational intervention(s), marketed product(s), placebo, or medical device(s) intended to be administered to a study participant according to the study protocol.

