3 STATISTICAL ANALYSES

3.1 GENERAL CONSIDERATIONS

In general, continuous data will be summarized using the number of observations available, mean, standard deviation (SD), median, interquartile range (Q1, Q3), minimum, and maximum.

Categorical and ordinal data will be summarized using the count and percentage of participants.

Efficacy data will be analyzed in the randomized and treated population except the primary endpoint which will be analyzed in the mITT population, and safety data will be analyzed in the safety population, unless specified otherwise.

In Part A, baseline values are defined as follows. The baseline value of NfL is defined as the lower value of screening and Day 1 visits if the number of gd-enhancing T1 lesion at Day 1 is greater than zero, otherwise it will be the average values of the assessments on screening and Day 1 visits prior to the first dose of the study intervention. The baseline values of EDSS and PD biomarkers other than NfL are defined as the average of the screening and Day 1 visit values prior to the first dose of the study intervention. If one of the values for the above assessments at screening and Day 1 is missing, the non-missing value will be used as the baseline value. For the other efficacy and safety assessments, the baseline values are defined as the last available value before the first dose of the study intervention. For the C-SSRS, the baseline value will be the worst assessment between the past 6 months evaluation at screening and the since last visit evaluation on Day 1. For participants randomized but not treated, the baseline value is defined as the last available value before randomization. Unless otherwise indicated, 2-sided p-values and 95% confidence intervals [CI(s)] will be provided for efficacy assessment of treatment differences. Unless otherwise specified, analyses will be performed by initial intervention group, ie, placebo or SAR443820 20 mg QD (and overall for baseline and demographics characteristics).

In Part B, efficacy analyses will be conducted accumulatively according to the treatment group allocated by randomization in Part A (ie, placebo/SAR443820 20 mg QD versus SAR443820 20 mg QD/ SAR443820 20 mg QD). Baseline values defined above for Part A will be used as the baseline in the efficacy analyses for Part B, unless otherwise noted. Safety analyses in Part B are specified in [Section 3.6](#).

Observation period

The observation period for safety will be divided into 4 segments:

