3.6 SAFETY ANALYSES

All safety analyses will be performed on the safety population as defined in [Section 2](#), unless otherwise specified, using the following common rules:

- The analysis of the safety variables will be essentially descriptive, and no testing is planned.
- Safety data in participants who do not belong to the safety population (eg, exposed but not randomized) will be provided separately.

In Part A, the safety analyses will be carried out with participants by the actual treatment received, irrespective of the treatment the participant has been randomized to.

Part A + Part B Safety Analyses

For categorical safety measures, such as AE, PCSA, shift summaries, data throughout both Part A and Part B will be summarized in three groups:

- Placebo/SAR443820 group includes participants who actually received placebo in Part A and SAR443820 in Part B. For participants in this group, only the data during SAR443820 exposure in Part B will be summarized. The baseline will be defined as the last available value prior to the first dose of SAR443820 in Part B.
- SAR443820/SAR443820 group includes participants who actually received SAR443820 in Part A, regardless of whether they entered Part B. For participants in this group, all data during SAR443820 exposure will be summarized. The baseline will be defined as the last available value prior to the first dose of the study intervention (same baseline defined for Part A in [Section 3.1](#)).
- Overall SAR443820 group includes participants from Placebo/SAR443820 group and SAR443820/SAR443820 group.

For continuous safety measures collected at longitudinal time point, such as labs and vital signs, data throughout both Part A and Part B will be summarized in two groups:

- Placebo/SAR443820 group includes participants who actually received placebo in Part A, regardless of whether they enter Part B. For participants in this group, all data during the on-treatment period of Part A and Part B will be summarized at each protocol scheduled visit. The baseline will be defined as the last available value prior to the first dose of study intervention (same baseline defined for Part A in [Section 3.1](#)).

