3.6.1 Extent of exposure

The extent of IMP exposure will be assessed by the duration of IMP exposure and summarized within the safety population.

Duration of IMP exposure

Duration of IMP exposure in Part A is defined as last IMP administration date in Part A – first IMP administration date + 1 day, regardless of unplanned intermittent discontinuations. If the date of the last dose of IMP in Part A is missing, the duration of IMP exposure in Part A will be left as missing.

Duration of cumulative SAR443820 exposure in Part A + Part B is defined as the last dose date of SAR443820 – first dose date of SAR443820 +1 day, regardless of unplanned intermittent discontinuations. If the last dose date of SAR443820 is missing, this duration will be left as missing.

Duration of IMP exposure in Part A will be summarized quantitatively and categorically by the treatment group participants actually received in Part A (Placebo versus SAR443820):

- > 0 and \leq 12 weeks
- > 12 and \leq 24 weeks
- > 24 and \leq 36 weeks
- > 36 and \leq 48 weeks
- > 48 weeks

Duration of cumulative SAR443820 in Part A + Part B will also be summarized quantitatively and categorically by actual treatment (Placebo/SAR443820, SAR443820/SAR443820 and overall) within the safety population:

- > 0 and \leq 12 weeks
- > 12 and \leq 24 weeks
- > 24 and \leq 36 weeks
- > 36 and \leq 48 weeks
- > 48 and \leq 72 weeks
- > 72 and \leq 96 weeks
- > 96 weeks

Additionally, the cumulative duration of treatment exposure (expressed in participant-years) will be provided for Part A and Part A + Part B separately.

Treatment compliance

A given administration will be considered noncompliant if the participant did not take the number of administrations as required by the protocol. No imputation will be made for participants with missing or incomplete data.

Percentage of treatment compliance for a participant will be defined as the number of administrations that the participant was compliant divided by the total number of administrations that the participant was planned to take from the first administration of IMP up to the actual last administration of IMP.

Treatment compliance will be summarized quantitatively and categorically (<80%, \geq 80%) for Part A and Part A + Part B using the similar format as stated above for exposure.

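### The as-treated rule in SAP Section 2 is not limited to Part A, so as worded it relabels every placebo participant who enters Part B as SAR443820; only descriptive outputs are exposed, chiefly the Part A biomarker summary

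*SAP*

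**What the plan says.** SAP Section 2, after the populations table, gives one rule for participants with two interventions: "For participants receiving more than one study intervention during the study, the intervention group for as-treated analyses will be SAR443820 20 mg QD". It has no limit to Part A and no exception for the planned move to open-label drug.

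Three other statements fix its reach:
- Protocol Section 6: "Study intervention is defined as any investigational intervention(s), marketed product(s), placebo, or medical device(s) intended to be administered to a study participant". Placebo is therefore a study intervention.
- SAP 1.1: "All participants will receive 20 mg QD SAR443820 in Part B".
- SAP Table 3, for both the safety and PK populations: "Participants will be analyzed according to the intervention they actually received".

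The safety section groups people differently. Its Part A sentence reads "In Part A, the safety analyses will be carried out with participants by the actual treatment received, irrespective of the treatment" assigned at randomization. For categorical safety measures over Parts A and B, "Placebo/SAR443820 group includes participants who actually received placebo in Part A and SAR443820 in Part B". SAP 3.6.1 summarizes Part A exposure "by the treatment group participants actually received in Part A (Placebo versus SAR443820".

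Two as-treated summaries sit outside Section 3.6. SAP 3.7.2 summarizes the eight biomarkers other than sNfL in Part A, by actual treatment group, in the safety population. SAP 3.7.1 summarizes plasma concentrations by study intervention in the PK population and covers everyone who received SAR443820.

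**The concern.** A placebo participant who takes the first open-label dose has received two study interventions during the study. The Section 2 rule then places that person in the SAR443820 group for as-treated analyses, with nothing to confine this to Part B data. A rule that looks meant for dosing errors in the blinded period also catches the planned crossover.

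At stake is the column in which placebo-period data appear in descriptive as-treated outputs. The biomarker summary is the most exposed. The same markers are analysed as tertiary endpoints in the randomized and treated population, by allocated group (SAP 3.4.2 and Table 3). If the Section 2 rule were programmed literally into SAP 3.7.2, the report would hold two Part A outputs for the same marker and visit with different columns, one of them counting placebo-period data as SAR443820.

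**Working it through.** The plan gives no figure to reproduce here, so the check is mainly one of text, followed by a count.

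**Does the rule catch planned rollovers?**
1. Placebo is a study intervention (Protocol Section 6).
2. The study comprises Parts A and B (SAP 1.1), and the on-study period in SAP 3.1 runs from randomization to the end of the study. Part B therefore lies within the study.
3. Everyone in Part B receives SAR443820 (SAP 1.1).
4. So every placebo participant dosed in Part B meets the rule.

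**Where does other text settle the group?**

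| Output | Grouping text | Tied expressly to Part A receipt? |
|---|---|---|
| Part A + Part B safety (SAP 3.6) | sequence groups by what was received in Part A | Yes |
| Part A exposure (SAP 3.6.1) | treatment received in Part A | Yes |
| Part A safety (SAP 3.6, general sentence) | actual versus randomized treatment, in Part A | Implied |
| Part A biomarkers (SAP 3.7.2) | actual treatment group, in Part A | Implied |
| PK concentrations (SAP 3.7.1) | study intervention; everyone who received SAR443820 | No, though scheduled sampling is in Part A only (Protocol 8.4) |

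The general default in SAP 3.1 is "Unless otherwise specified, analyses will be performed by initial intervention group". The biomarker and PK summaries are specified as as-treated, so that default does not settle them.

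**Illustration: literal use in the Week 48 biomarker summary**

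Inputs: 84 per arm (SAP 1.1) and 17% dropout (SAP Section 4, the sample-size allowance, not a rollover forecast). Assumptions: equal dropout in both arms, no Week 48 sample from dropouts, and a fraction *r* of Part A completers entering Part B.

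- Completers per arm: *c* = 84 × (1 − 0.17) = 69.7.
- SAR443820 column = *c* + *rc*; placebo column = *c* − *rc*.
- Placebo-period share of the SAR443820 column = *r*/(1 + *r*), whatever the dropout rate.

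| *r* (assumed) | SAR443820 column | Placebo column | Placebo-period share |
|---|---|---|---|
| 1.0 | 139.4 | 0 | 50.0% |
| 0.9 | 132.5 | 7.0 | 47.4% |
| 0.8 | 125.5 | 13.9 | 44.4% |
| Grouped by Part A receipt | 69.7 | 69.7 | 0% |

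All of the relabelled Week 48 data come from the placebo period, because the Part A schedule requires Week 48 assessments to be completed before the first open-label dose.

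**The case against.** The strongest reply is that no sensible reader would apply the sentence this way. The SAP's specific groupings show the intent. The phrase *in Part A* in SAP 3.7.2 is most naturally read as the treatment taken in Part A, and it closely matches the Part A safety sentence in SAP 3.6. The protocol points the same way: 9.2.1 defaults to the initial intervention group, 9.2.6 presents safety by initial treatment group separately for Parts A and B, and 9.2.7 summarizes concentrations in the SAR443820 dose group. The SAP's list of changes from the protocol records no change of grouping. A Part A table with an empty placebo column would also be noticed.

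Most of this stands. It makes misapplication unlikely, and it rules out three stronger readings that a reader might infer:
- *That the rule empties the Placebo/SAR443820 safety group.* It does not. SAP 3.6 defines membership by what was received in each part, which a label from Section 2 cannot alter.
- *That the biomarker and PK summaries have no other guidance.* This is too strong, given the wording of SAP 3.7.2 and the three protocol sections. What is missing is an express statement.
- *That a stated share of the PK group would be placebo samples.* That requires placebo samples to be assayed and reported, which the documents do not say, so no PK figure is given.

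What the reply does not remove is that Section 2 states an explicit rule whose plain wording contradicts the later sections.

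**Conclusion.** The point holds as a minor wording conflict. As written, the Section 2 rule relabels every placebo participant who enters Part B, against the groupings in SAP 3.6 and 3.6.1. Those specific definitions should govern the safety tables. The Part A biomarker summary is the main output left to inference, with the PK summary second.

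The primary, secondary and tertiary efficacy analyses use the allocated group and are unaffected. The column counts show what literal programming would do under the stated dropout and rollover assumptions. They are not an expected result and say nothing about how likely the error is.

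**What to change.** Amend the SAP Section 2 sentence in three ways:
- limit it to participants who receive more than one study intervention during Part A, and to as-treated analyses of Part A, keeping SAR443820 20 mg QD as the assigned group;
- add that open-label SAR443820 in Part B does not change the Part A group;
- refer to Section 3.6 for Part A + Part B groupings.

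Then add *received in Part A* to the Part A sentence in Section 3.6, to both grouping phrases in Section 3.7.1, and to the grouping in Section 3.7.2.

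The amended rule still covers a placebo participant given SAR443820 during Part A. Apart from such cases, the Part A groups stay at 84 and 84 if all randomized participants are treated. The SAP would still have both an as-treated and an as-randomized biomarker output, but their columns would differ only for participants whose Part A treatment differed from their allocation.

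The cost is one sentence and short qualifiers in three sections. No new data or derived variable is needed, since SAP 3.6.1 already requires the treatment received in Part A.
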